6.6 PHARMACOKINETIC AND PHARMACODYNAMIC ANALYSES

Sparse PK samples will be collected and analyzed for venetoclax and fulvestrant concentrations in the venetoclax arm. The PK data will be summarized after appropriate grouping. Venetoclax and/or fulvestrant results may be incorporated into a nonlinear mixed-effect population PK model to estimate the PK parameters. Pharmacodynamic modulation of BCL-2 and estrogen-responsive genes will be evaluated in optional on-treatment biopsies relative to pre-dose biopsies.

Additional PK analyses will be conducted as appropriate.

6.7 EXPLORATORY OBJECTIVES

6.7.1 Patient-Reported Outcome Analyses

Summary statistics (i.e., mean, standard deviation, median, minimum, maximum, and range) of linear transformed scores will be reported for all scales (symptom, functional domains, and single items) of the EORTC QLQ-C30 according to the EORTC scoring manual guidelines (Fayers et al. 2002) for each assessment timepoint. Line charts depicting the mean changes \pm *standard deviations* of items and scales over time will be provided for each treatment arm from the baseline assessment.

Previously published minimally important differences will be used to identify meaningful change from baseline within each treatment group on the functional and disease/treatment related symptoms scales (Osoba et al. 1998). In the event of incomplete data, for all questionnaire subscales, if more than 50% of the constituent items are completed, a prorated score will be computed consistent with the scoring manuals and validation papers. For subscales with less than 50% of the items completed, the subscale will be considered as missing.

To evaluate patient-reported HRQoL while on study treatment, descriptive analysis of the mean and mean change from patients' baseline GHS/HRQoL scale score, which consists of Questions 29 and 30 of the EORTC QLQ-C30 (see [Appendix 5](#)), will be assessed by cycle and independently within each cohort. GHS/HRQoL will also be calculated as the number, proportion, and 95% CI of patients with a change in score *reflecting clinically meaningful deterioration, defined as a decrease of 10 points or more (Osoba et al., 1998).*

To evaluate patient-reported pain while on study treatment, descriptive analysis of the mean and mean change from patients' baseline pain scale score, which consists of Questions 9 and 19 of the EORTC QLQ-C30 (see [Appendix 5](#)), will be assessed by cycle and independently within each cohort. Additionally, the pain scale data will also be calculated as the number, proportion, and 95% CI of patients with *clinically meaningful pain progression defined by an increase in score of 10 points or more (Osoba et al., 1998).*

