
 To assess potential drug-drug interactions between venetoclax and fulvestrant 	
 Plasma concentrations or PK parameters of venetoclax and fulvestrant given in combination compared with these agents given alone (based on historical data)
Biomarker Objectives:	

 To evaluate predictive, prognostic, and pharmacodynamic biomarkers in tumor tissue and plasma associated with disease activity, response to treatment, or resistance to venetoclax in combination with fulvestrant 	
 Baseline BCL-2 protein levels as measured by IHC correlating with clinical response measures Expanded biomarkers (see Table 2) measured at baseline, on-treatment, and at end of treatment relative to clinical response measures

Objectives	Corresponding Endpoints
PRO Objectives:	

 To evaluate PROs of function, disease/treatment-related symptoms, and GHS/overall HRQoL associated with venetoclax in combination with fulvestrant compared with fulvestrant alone To evaluate and compare PROs of disease-related pain in venetoclax in combination with fulvestrant compared with fulvestrant alone 	
 Mean and mean changes from baseline scores in functional (i.e., role, physical, emotional, and social), disease/treatment-related symptoms, and GHS/HRQoL by cycle as assessed by the scales (Questions 29 and 30) of the EORTC QLQ-C30 Change in baseline pain score as assessed by the pain scale (Questions 9 and 19) of EORTC QLQ-C30

AEs = adverse events; AESI = adverse events of special interest; BCL-2=B-cell lymphoma 2; CR = complete response; DOR = duration of response; EORTC = European Organisation for Research and Treatment of Cancer; GHS = global health status; HRQoL = health-related quality of life; IHC=immunohistochemistry; OS = overall survival; PFS = progression-free survival; PK = pharmacokinetic; PR = partial response; PRO = patient-reported outcome; QLQ-C30 = Quality of Life Questionnaire Core 30; RECIST v1.1 = Response Evaluation Criteria in Solid Tumors Version 1.1; SAEs = serious adverse events; SD = stable disease.

Table 2 Biomarkers for Exploratory Research

Proposed Biomarkers	Sample Type	Timing
ctDNA	Plasma	Pre-dose at baseline and subsequent time points during treatment (see Appendix 1)

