- **Control arm:** fulvestrant 500 mg administered as two 250-mg IM injections on Cycle 1 Days 1 and 15, and then on Day 1 of each subsequent 28-day cycle. No crossover to the venetoclax arm is permitted.

Tumor assessments will be conducted for all patients at screening and at every 8 weeks (± 5 days) from the date of randomization until Week 24 (± 5 days) and every 12 weeks (± 5 days) thereafter. Tumor assessments will be conducted regardless of dose delays or early discontinuation, until investigator-assessed disease progression (as specified below), the predefined end of the study (Section 3.3), or until death, whichever occurs first.

Study treatment for each patient will continue until disease progression, unacceptable toxicity, withdrawal of consent, death, or study termination by the Sponsor, whichever occurs first.

Diagnosis of disease progression should be supported by radiology assessments as per RECIST v1.1. All patients who are discontinued from all study treatment will return for a study drug discontinuation visit 28 days (+3 days) after the last dose of study treatment.

Patients who are discontinued from study treatment for reasons other than disease progression and have started follow-on treatment will be followed for survival approximately every *3 months, or more frequently*, until death, loss to follow-up, withdrawal of consent, or study termination by the Sponsor, whichever occurs first.

Patients who are discontinued from study treatment for reasons other than disease progression and have not started follow-on treatment will be followed for disease status every 8 weeks (± 5 days) from the date of randomization until Week 24 (± 5 days) and then every 12 weeks (± 5 days) thereafter until disease progression, death, loss to follow-up, withdrawal of consent, or study termination by the Sponsor, whichever occurs first.

[figure not shown]
After disease progression, patients will be followed for survival and subsequent anti-cancer therapies approximately every *3 months, or more frequently*, until death, loss to follow-up, withdrawal of consent, or study termination by the Sponsor, whichever occurs first.

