3.4.6 Rationale for Patient-Reported Outcome Assessments

As MBC is not curable with currently approved and available therapies, the main goals of treatment are to prolong survival and maintain or improve quality of life (Cardoso et al. 2012). Disease symptoms are dependent on sites of metastases (Irvin et al. 2011), and patients can have bone involvement. Examining and measuring patients' pain, their global health status (GHS)/overall health-related quality of life (HRQoL), as well as their treatment-related symptoms and their interference with daily life is important and will be assessed using validated PRO assessments.

The European Organisation for Research and Treatment of Cancer Core Quality of Life Questionnaire-Core 30 (EORTC QLQ-C30) will be administered to patients to assess disease/treatment-related symptoms, functioning, and HRQoL (see Section 4.5.9 and Appendix 5).

In addition, for patients with metastatic disease, pain can be a serious symptom. Therefore, measuring pain and the progression of pain and its impact on patients are important; thus, this symptom will be assessed using the pain scale from the EORTC QLQ-C30.

The EORTC QLQ-C30 will be assessed at baseline (Cycle 1, Day 1), at Day 1 of each subsequent cycle, and at the treatment discontinuation visit (see Appendix 1). The PRO data will be collected using paper questionnaires completed at the clinic site visit.

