4.5.9 Patient-Reported Outcomes

4.5.9.1 EORTC QLQ-C30 Background

The EORTC QLQ-C30 (see [Appendix 5](#)) is a validated and reliable self-reported measure (Aaronson et al. 1993; Sprangers et al. 1996; Fitzsimmons et al. 1999) consisting of 30 questions that assess 5 aspects of patient functioning (physical, emotional, role, cognitive, and social), 8 symptoms (fatigue, nausea and vomiting, pain, dyspnea, insomnia, appetite loss, constipation, and diarrhea), financial difficulties, and GHS/HRQoL with a recall period of the previous week. The EORTC QLQ-C30 data will be scored according to the EORTC scoring manual (Fayers et al. 2002). Scale scores will be obtained for each of the multi-item and single-items scales by using a linear transformation for standardization of the calculated raw score. The EORTC QLQ-C30 takes approximately 10 minutes to complete.

To fully characterize venetoclax with fulvestrant compared with single-agent fulvestrant as a second-line treatment in patients with MBC, PRO data will be collected using the EORTC QLQ-C30. Specifically, the GHS/overall HRQoL scale score (Questions 29 and 30) will be used to assess patients' overall HRQoL and the pain (Questions 9 and 19)

scale of the EORTC QLQ-C30 will be used evaluate the proportion of patients with disease-related pain of venetoclax+fulvestrant compared with fulvestrant alone.

The EORTC QLQ-C30 will be administered to patients to assess pain, disease/treatment-related symptoms, functioning, and HRQoL (see Section 4.5.9.2 and Appendix 5).

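### The patient-reported outcome objectives compare the arms, but Section 6.7.1 plans only within-arm description, so GHS and pain have no between-arm estimate

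*Combined protocol and SAP*

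**What the plan says.** **Objectives.** Table 1 (Section 2, repeated in the synopsis) has the pain objective "To evaluate and compare PROs of disease-related pain in venetoclax in combination with fulvestrant compared with fulvestrant alone". The broader objective covers function, symptoms and "GHS/overall HRQoL associated with venetoclax in combination with fulvestrant compared with fulvestrant alone". Section 4.5.9.1 gives the pain items the same comparative purpose: the "scale of the EORTC QLQ-C30 will be used evaluate the proportion of patients with disease-related pain of venetoclax+fulvestrant compared with fulvestrant alone".

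**Analysis.** Section 6.7.1 plans summary statistics at each timepoint, line charts of mean change for each arm, and, for GHS and pain, means and mean changes that "will be assessed by cycle and independently within each cohort". It adds the number, proportion and 95% CI of patients whose score worsens by at least 10 points. Cohort can only mean treatment arm here. No difference, ratio, model or between-arm interval is specified.

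**Collection.** The questionnaire is given at baseline, "at Day 1 of each subsequent cycle, and at the treatment discontinuation visit" (Section 3.4.6; Appendix 1 agrees). Section 3.1 says when treatment ends: "Study treatment for each patient will continue until disease progression, unacceptable toxicity, withdrawal of consent, death, or study termination by the Sponsor".

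**Missing data.** The only rule is at item level: "if more than 50% of the constituent items are completed, a prorated score will be computed". Nothing is said about missing forms, completion rates, the analysis set, or the denominator and timepoint for the 10-point proportions.

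**The concern.** A comparative objective needs an estimate of the difference between arms with its uncertainty. Two columns of within-arm means leave the reader to compare by eye, without an interval and without adjustment for baseline differences between arms. An interval around each arm's own proportion does not replace an interval for the difference.

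The second issue is who contributes to each column. Collection ends soon after treatment does, and treatment ends for progression, toxicity or death, all plausibly related to quality of life. That each later cycle describes only patients still answering is an inference from the visit schedule, the on-treatment wording and the lack of a form-level rule; the plan does not state it. If the arms lose patients at different rates or for different reasons, the columns describe differently selected groups.

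At stake is whether this part of the trial can say anything about the effect of adding venetoclax on how patients feel. Section 3.4.6 itself names quality of life among the main aims of treatment in this disease.

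**Working it through.** **1. Objective against analysis.** Table 1 and Section 4.5.9.1 ask for the combination against fulvestrant alone. Section 6.7.1 supplies only within-arm quantities. Elsewhere the plan does specify contrasts: CIs for the difference in clinical benefit rate (6.4.1), the same analysis for response (6.4.2.2), and hazard ratios for PFS and OS (6.4.2.1, 6.4.2.4).

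**2. Inputs.** The documents state no PRO figure to reproduce. Their one design calculation is the 80% CI for clinical benefit with 50 per arm at 40% and 60%: 1.2816 × √(0.4×0.6/50 + 0.6×0.4/50) = 12.6 points, and a continuity correction of 0.5 × (1/50 + 1/50) = 2.0 gives 14.6, which matches the stated 15%. The sample size and the two rates are used below. GHS SD, correlations and retention are assumptions, because the documents give none.

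**3. Raw means, no true difference.** Suppose a fraction p is retained, selected on a latent variable with correlation ρ to the score. The retained mean shifts by ρ × SD × φ(z_p)/p, where z_p is the p-quantile of the standard normal. For p = 0.4, φ(z_p)/p = 0.3863/0.4 = 0.966; for p = 0.6 it is 0.3863/0.6 = 0.644. Borrowing the planning rates as retention (40% control, 60% venetoclax):

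| SD | ρ | Control shift | Venetoclax shift | Venetoclax minus control |
|---|---|---|---|---|
| 20 | 0.2 | 3.9 | 2.6 | −1.3 |
| 20 | 0.5 | 9.7 | 6.4 | −3.2 |
| 25 | 0.2 | 4.8 | 3.2 | −1.6 |
| 25 | 0.5 | 12.1 | 8.0 | −4.0 |

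With ρ = 0, or with equal retention and selection in both arms, the between-arm distortion is zero. A simulation at ρ = 0.3 and 0.5 gave −2.1 to −4.1.

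**4. Mean changes.** Simulations with no true difference, dropout depending on the last score, and about 50% against 29% retained gave raw means 1.0 to 3.8 points in favour of the faster-dropout arm, but mean changes 0.0 to 1.4 points against it. The sign turns because selection acts directly on baseline and early scores and only indirectly on the latest one, so the survivors' baseline is inflated more than their current score. If dropout instead followed the change itself, the formula in step 3 would apply to changes as well.

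**5. The 10-point proportion.** Section 6.7.1 gives no timepoint. At a fixed cycle, the number of forms a patient completed has no direct effect. Read as worsening at any time, with no true change and within-patient correlation 0.6, the threshold is crossed by 43% of patients with 2 post-baseline forms and 65% with 6: a gap of 65 − 43 = 22 percentage points from form count alone.

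**6. Precision of a between-arm mean difference.** The half-width is 1.96 × SD × √(1/n₁ + 1/n₂), before any gain from baseline adjustment. With 50 per arm: 1.96 × 20 × 0.2 = 7.8, and 9.8 at SD 25. With 20 against 30: 1.96 × 20 × 0.2887 = 11.3, and 14.1 at SD 25. Power for a 10-point difference at two-sided 5% is 71% to 52% with 50 per arm and 41% to 28% with 20 against 30. Relative to raw change scores, baseline adjustment multiplies the variance by (1 − r²)/(2(1 − r)) = (1 + r)/2, which is 0.7 to 0.8 at r = 0.4 to 0.6, a saving of 20 to 30%.

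**The case against.** Section 6.7 is headed exploratory and Section 6.9 calls the study hypothesis-generating. The endpoints listed in Table 1 are themselves means and changes, which Section 6.7.1 delivers. The stated target is also on-treatment: "To evaluate patient-reported HRQoL while on study treatment, descriptive analysis of the mean and mean change". By-cycle means among treated patients describe that. Collection includes the discontinuation visit, and a patient who stops venetoclax may stay on fulvestrant (Section 5.1.3.3), so stopping venetoclax for toxicity need not end it. With about 50 per arm, intervals would be wider than any distortion computed above, and a model added after the read-out is post hoc.

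Most of this stands and lowers the weight of the point. None of it supplies the missing comparison: an exploratory or on-treatment objective that is worded as a comparison still needs an estimate. Rewording the objectives as descriptive would remove the mismatch, but would leave the comparative question unanswered when the data to address it exist.

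A reader might go further and infer that dropout does distort these means and would hide a quality-of-life cost of venetoclax. The documents do not support that. They give no PRO SD, correlation or completion rate; their only planning rates, 40% and 60% clinical benefit, would suggest slower dropout on venetoclax; and for the change scores that the plan also reports, the simulated artefact works against the faster-dropout arm.

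**Conclusion.** The mismatch is established from the text: the GHS/HRQoL and pain objectives are comparative, and the plan as written produces no between-arm estimate or interval for either.

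The dropout issue is a vulnerability, not a demonstrated bias. Under the assumptions above it amounts to a few points for raw means and about 1 point or less, in the opposite direction, for mean changes. It is zero if retention and selection are equal, and neither size nor sign can be fixed from the documents. The form-count problem arises only if the 10-point proportion means worsening at any time, which Section 6.7.1 neither states nor excludes.

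The point is of moderate weight: it limits what the PRO data can answer and does not touch the primary endpoint.

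**What to change.** In Section 6.7.1:

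- For GHS and pain, add a repeated-measures model for change from baseline with baseline score, arm, cycle, arm-by-cycle, BCL-2 status and number of prior lines. Report the arm difference with 95% CI over the cycles with adequate numbers, as an exploratory estimate and not a test.
- For the 10-point worsening endpoint, fix the timepoint or window and the denominator, and give the between-arm difference in proportions with 95% CI.
- Show questionnaire completion by arm and cycle.
- State the missing-at-random assumption, how questionnaires after the venetoclax stop of 8 October 2020 are handled, and that the model was added after the primary read-out.
- Keep the descriptive tables and charts.

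**Cost:** a little extra analysis on data already collected, no new visits, and reliance on missing at random, which these data cannot verify. The intervals will be wide, as the precision calculation shows, and should be presented as such.

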6.8 BIOMARKER ANALYSES

Exploratory analyses of biomarkers related to tumor biology and the mechanisms of action of venetoclax will be conducted. Analyses will assess prognostic and/or predictive value of candidate biomarkers. The association between candidate biomarker measures of efficacy, with treatment and independent of treatment, will be explored to assess potential predictive and prognostic value, respectively. The effects of baseline prognostic and potentially predictive characteristics, including BCL-2 expression, BCL-2 family member transcript and/or gene signatures, as well as ctDNA profiles on efficacy outcomes, will be evaluated using univariate and/or multivariate statistical methods such as Cox regression and logistic regression.

6.9 OPTIONAL INTERIM ANALYSES

Given the hypothesis-generating nature of this study, the Sponsor may choose to conduct up to two interim efficacy analyses. The decision to conduct an optional interim analysis and the timing of the analysis will be documented in the Sponsor's trial master file prior to the conduct of the interim analysis. The interim analysis will be performed and interpreted by members of the Sponsor study team and appropriate senior management personnel.

7. DATA COLLECTION AND MANAGEMENT

7.1 DATA QUALITY ASSURANCE

The Sponsor will be responsible for data management of this study, including quality checking of the data. Data entered manually will be collected via EDC through use of eCRFs. Sites will be responsible for data entry into the EDC system. In the event of discrepant data, the Sponsor will request data clarification from the sites, which the sites will resolve electronically in the EDC system.

The Sponsor will produce an EDC Study Specification document that describes the quality checking to be performed on the data. Central laboratory data and any other externally generated electronic study data will be sent directly to the Sponsor, using the Sponsor's standard procedures to handle and process the electronic transfer of these data.

eCRFs and correction documentation will be maintained in the EDC system's audit trail. System backups for data stored by the Sponsor and records retention for the study data will be consistent with the Sponsor's standard procedures.

PRO data will be collected on paper questionnaires. The data from the questionnaires will be entered into the EDC system by site staff.

7.2 ELECTRONIC CASE REPORT FORMS

eCRFs are to be completed through use of a Sponsor-designated EDC system. Sites will receive training and have access to a manual for appropriate eCRF completion. eCRFs will be submitted electronically to the Sponsor and should be handled in accordance with instructions from the Sponsor.

All eCRFs should be completed by designated, trained site staff. eCRFs should be reviewed and electronically signed and dated by the investigator or a designee.

At the end of the study, the investigator will receive patient data for his or her site in a readable format on a compact disc that must be kept with the study records. Acknowledgement of receipt of the compact disc is required.

7.3 PATIENT-REPORTED OUTCOME DATA

Patients will use paper forms to record PRO data. PROs must be stored in the appropriate patient file as source data and maintained at the study site.

7.4 SOURCE DATA DOCUMENTATION

Study monitors will perform ongoing source data verification and review to confirm that critical protocol data (i.e., source data) entered into the eCRFs by authorized site personnel are accurate, complete, and verifiable from source documents.

Source documents (paper or electronic) are those in which patient data are recorded and documented for the first time. They include, but are not limited to, hospital records, clinical and office charts, laboratory notes, memoranda, patient-reported outcomes, evaluation checklists, pharmacy dispensing records, recorded data from automated instruments, copies of transcriptions that are certified after verification as being accurate and complete, microfiche, photographic negatives, microfilm or magnetic media, X-rays, patient files, and records kept at pharmacies, laboratories, and medico-technical departments involved in a clinical trial.

Before study initiation, the types of source documents that are to be generated will be clearly defined in the Trial Monitoring Plan. This includes any protocol data to be entered directly into the eCRFs (i.e., no prior written or electronic record of the data) and considered source data.

Source documents that are required to verify the validity and completeness of data entered into the eCRFs must not be obliterated or destroyed and must be retained per the policy for retention of records described in Section 7.6.

To facilitate source data verification and review, the investigators and institutions must provide the Sponsor direct access to applicable source documents and reports for trial-related monitoring, Sponsor audits, and IRB/EC review. The study site must also allow inspection by applicable health authorities.

